### 465 **Suspected Unexpected Serious Adverse Event (SUSAR):**

466 Mountain Diabetes and Endocrine Center will inform the appropriate regulatory authorities, the  
467 IRB, and Novo Nordisk of trial product-related SUSARs in accordance with reporting  
468 requirements and GCP guidelines.

469

470 **Serious Adverse Drug Reaction (SADR):**

471 An adverse drug reaction (ADR) is an adverse event for which a causal relationship  
472 (Possible/Probable relation) between the study drug and the occurrence of the event is  
473 suspected. The ADR will be classified as **serious** if it meets one or more of the seriousness  
474 criteria.

475

476 **Medical Events of Special Interest (MESI):** A MESI is (1) a medication error (e.g. wrong drug  
477 administration or wrong route of administration) or (2) a suspected transmission of an  
478 infectious agent via the product

479

480 **Non-Serious Adverse Event:**

481 A non-serious AE is any AE which does not fulfill the definition of an SAE.

482

483 **Severity Assessment Definitions:**

- 484 • Mild: Transient symptoms, no interference with the subject's daily activities
- 485 • Moderate: Marked symptoms, moderate interference with the subject's daily activities
- 486 • Severe: Considerable interference with the subject's daily activities, unacceptable

487

488 **Relationship to study medication Assessment Definitions:**

- 489 • Probable: Good reason and sufficient documentation to assume a causal relationship
- 490 • Possible: A causal relationship is conceivable and cannot be dismissed
- 491 • Unlikely: The event is most likely related to an etiology other than the trial product

492

493 **Outcome Categories and Definitions:**

494

- 495 • Recovered: Fully recovered or by medical or surgical treatment the condition has returned to  
496 the level observed at the first trial related activity after the subject signed the informed  
497 consent
- 498 • Recovering: The condition is improving and the subject is expected to recover from the event.  
499 This term should only be used when the subject has completed the trial
- 500 • Recovered with sequelae: As a result of the AE, the subject suffered persistent and  
501 significant disability/incapacity (e.g. became blind, deaf, paralysed). Any AE recovered with  
502 sequelae will be rated as an SAE
- 503 • Not recovered
- 504 • Fatal
- 505 • Unknown

506

507 **Collection, Recording, Evaluating, and Reporting of Adverse Events**

508

509 All events meeting the definition of an adverse event will be collected, reported, and evaluated  
510 from the first trial-related activity after the subject has signed the informed consent and until  
511 the end of the post-treatment follow-up period as stated in the protocol. All adverse events

512 resulting from incorrect storage or usage of study product as per product labelling, if applicable,  
513 will be reported to the appropriate institutions (7,8). The investigator will copy Novo Nordisk  
514 when expediting SAE information to health authorities and will report all SAEs related to Novo  
515 Nordisk products to the local Novo Nordisk affiliate safety department. SAE submission to  
516 Novo Nordisk will be within 15 days from the investigator's first awareness of the event.

517

#### 518 **Follow-up of Adverse Events**

519

520 **During and following a subject's participation in this clinical trial, Mountain Diabetes and**  
521 **Endocrine Center, its investigators and site staff, will provide adequate medical care to the**  
522 **study subject for any study-related adverse events, including clinically significant laboratory**  
523 **values related to the study. This medical care for study subjects will be provided regardless of**  
524 **their insurance status.**

525

526 **All adverse events classified as serious or severe or possibly/probably related to the trial**  
527 **product will be followed until the subject has recovered and all queries have been resolved.**

528 For cases of chronic conditions, follow-up until the outcome category is "recovered" is not  
529 required, as these cases can be closed with an outcome of "recovering" or "not recovered".

530 All other adverse events will be followed until the outcome of the event is "recovering" (for  
531 chronic conditions), or "recovered" or until the end of the post-treatment follow-up stated in  
532 the protocol, whichever comes first, and until all queries related to these AEs have been  
533 resolved.

534

#### 535 **Pregnancy**

536 Study subjects will be instructed to notify the site and study physician immediately if they  
537 become pregnant.

538

539 **Mountain Diabetes and Endocrine Center, its investigators and site staff, will report to Novo**  
540 **Nordisk any pregnancy occurring during the trial period. Reporting of pregnancy by the site**  
541 **will occur within the same timelines described above for reporting of Adverse Events.**

542

543 Pregnancy complications will be recorded as adverse event(s). If the infant has a congenital  
544 anomaly/birth defect this must be reported and followed up as a serious adverse event.

545

#### 546 **Precautions/ Insulin Over-dosage**

547 Study subjects will be prescribed glucagon kits and treatment of hypoglycemia will be reviewed  
548 with subjects upon enrolment into the study.

549

#### 550 **LIABILITY AND SUBJECT INSURANCE:**

551 **During and following a subject's participation in trial, Mountain Diabetes and Endocrine**  
552 **Center and the study physicians will provide adequate medical care to the study subject for**  
553 **any study-related adverse events, including clinically significant laboratory values related to**

554 the study. This medical care for study subjects will be provided regardless of their insurance  
555 status.

556  
557 **Mountain Diabetes and Endocrine Center and its investigators will be responsible for the**  
558 **conduct of the study and agree to defend, indemnify, and hold harmless Novo Nordisk, any of**  
559 **its parent companies, affiliates, or subsidiaries, and their respective officers, directors,**  
560 **employees, agents, representatives, distributors, salespersons, customers, licensees, and**  
561 **end-users from and against any claim, suit, demand, loss, damage, expense or liability**  
562 **imposed by any third party arising from or related to: (a) any breach of sponsor-investigator's**  
563 **obligations or representations; or (b) sponsor-investigator's negligent or grossly negligent use**  
564 **or willful misuse of the study drug, the results, or services derived therefrom. This**  
565 **indemnification shall not apply in the event and to the extent that a court of competent**  
566 **jurisdiction or a duly appointed arbiter determines that such losses or liability arose as a**  
567 **result of Novo Nordisk's gross negligence, intentional misconduct, or material breach of its**  
568 **responsibilities.**

569

#### 570 **EVALUABILITY OF SUBJECTS**

571 Only the principal investigator has the authority to exclude any subjects or data observations  
572 after the initiation of the study, initial selection of subjects, and beginning of data collection.  
573 Possible reasons for such actions might be (1) questionable validity or reliability of data  
574 collection or measurement techniques for a particular subject, (2) misrepresentation of initial  
575 selection criteria by a subject, or (3) changes in the health conditions of subjects that might  
576 affect the reliability or validity of measurements or accuracy of data collection procedures. The  
577 reasons for any such action will be carefully documented by the principal investigator and kept  
578 on file for the actionable subject.

579

#### 580 **PREMATURE TERMINATION OF STUDY**

581

582 The study will only be discontinued prematurely in the unlikely event of an unforeseen safety  
583 concern arising from the study protocol.

584

#### 585 **PUBLICATION PLAN**

586

587 Upon approval, the study will be registered with [www.clinicaltrials.gov](http://www.clinicaltrials.gov).

588

589 Upon study completion, the study results will be submitted in a manuscript to a peer-reviewed  
590 journal. It is anticipated that the study results will be of sufficient interest and importance to  
591 be presented at one or more national meetings, notably ADA, AACE and AADE.

592

#### 604 **APPENDIX: METHOD OF CONVERSION OF BASAL INSULIN BY CSII TO DEGLUDEC**

605

606 Upon randomization to insulin degludec, or upon crossover from CSII to insulin degludec, the  
607 first dose of insulin degludec will be administered on day one and a 50% temporary basal  
608 reduction of the insulin pump for 24 hours will be activated. After 24 hours, the insulin pump  
609 basal rate will be lowered to the lowest hourly infusion rate (0.025 units per hour or 0.05 units  
610 per hour for a total daily basal insulin dose of either 0.6 or 1.2 units per day) for the duration of  
611 the insulin degludec treatment arm, with the remainder of the basal insulin dose administered  
612 as a single daily Tresiba injection.

613  
614 The 24 hour basal insulin dose by CSII will be converted to degludec on a unit-for-unit basis.  
615 This is because both degludec and CSII are roughly equivalent methods with high efficiency  
616 (bioavailability) for delivery of a basal insulin dose. Although there are no head-to-head studies  
617 comparing basal insulin dose by CSII to degludec, clinical studies (and the experience of the  
618 investigator) suggest that the lowest basal insulin requirement for any given subject will be with  
619 either CSII or degludec compared to glargine, NPH or detemir.

620  
621 A comparison of insulin degludec to continuous subcutaneous infusion of insulin aspart for  
622 basal insulin delivery in type 1 diabetes:

#### 623 624 Visit Procedures

625

626 **Note: Assessment of hypoglycemia and capturing of AE's (including technical complaints and**  
627 **device site reactions) will be performed at each study visit, as well as diabetes education.**  
628

629 Visit 1 (Screening Visit): Obtain written informed consent; review inclusion/exclusion criteria;  
630 demography (including child bearing potential and tobacco use); medical history; record  
631 concomitant medications; vital signs (incl. height); complete physical examination; review  
632 download of Dexcom and pump; HbA1c, GlycoMark, CBC, comprehensive metabolic profile  
633 (CMP), lipid panel, urine microalbumin/creatinine ratio (LabCorp); pregnancy test (urine);  
634 review treatment of hypoglycemia; insert Dexcom sensor; provide a hypoglycemia/basal dose  
635 diary  
636

637 Phone Visit 2: Remind subject to insert new Dexcom sensor; assessment of infusion site  
638 reactions and occlusions; hypoglycemia assessment (insulin titration if required)

639  
640 Visit 3 (Randomization): Review of inclusion/exclusion criteria; vital signs; CGM and insulin  
641 pump downloads; HbA1c (POC - Afinion); insulin optimization/titration; dispensing of  
642 hypoglycemia/basal dose diary; Tresiba pen teaching (degludec arm only); dispense trial  
643 product; treatment questionnaires  
644  
645 Visit 4: Vital signs; pump and CGM downloads; insulin optimization/titration; assessment of  
646 infusion site reactions and occlusions; dispensing of hypoglycemia/basal dose diary  
647  
648 Visit 5: Vital signs; pump and CGM downloads; insulin optimization/titration; assessment of  
649 infusion site reactions and occlusions; dispense trial product; dispensing of hypoglycemia/basal  
650 dose diary; drug accountability and diabetes education.  
651  
652 Phone Visit 6: Ensure subject is changing insulin pump sites and CGM per protocol, assessment  
653 of infusion site reactions and occlusions; review of hypoglycemia (insulin titration if required)  
654  
655 Visit 7: Vital signs; pump and CGM downloads; assessment of infusion site reactions and  
656 occlusions; dispense trial product; dispensing of hypoglycemia/basal dose diary; drug  
657 accountability  
658  
659 Phone Visit 8: Ensure subject is changing insulin pump sites and CGM per protocol, assessment  
660 of infusion site reactions and occlusions; review of hypoglycemia (insulin titration if required)  
661  
662 Visit 9: Vital signs; pump and CGM downloads; assessment of infusion site reactions and  
663 occlusions; dispense trial product; dispensing of hypoglycemia/basal dose diary; drug  
664 accountability  
665  
666 Visit 10: Vital signs; pump and CGM downloads; assessment of infusion site reactions and  
667 occlusions; dispense trial product; dispensing of hypoglycemia/basal dose diary; drug  
668 accountability  
669  
670 Visit 11: Dexcom sensor insertion; assessment of infusion site reactions and occlusions, review  
671 of hypoglycemia/basal dose diary  
672  
673 Visit 12 (Cross-over Visit): Vital signs; complete physical examination; pump and CGM  
674 downloads; insulin optimization/titration; treatment crossover; Tresiba pen training (degludec  
675 arm only); HbA1c, GlycoMark, CBC, comprehensive metabolic profile (CMP), urine  
676 microalbumin/creatinine ratio (LabCorp); pregnancy test (urine); dispense trial product;  
677 treatment questionnaires; dispensing of hypoglycemia/basal dose diary; assessment of infusion  
678 site reactions and occlusions; drug accountability  
679  
680 Visit 13: Vital signs; pump and CGM downloads; insulin optimization/titration; assessment of  
681 infusion site reactions and occlusions; dispensing of hypoglycemia/basal dose diary  
682

683 Visit 14: Vital signs; pump and CGM downloads; insulin optimization/titration; assessment of  
684 infusion site reactions and occlusions; dispense trial product; dispensing of hypoglycemia/basal  
685 dose diary; drug accountability  
686  
687 Phone Visit 15: Ensure subject is changing insulin pump sites and CGM per protocol, assessment  
688 of infusion site reactions and occlusions; review of hypoglycemia (insulin titration if required)  
689  
690 Visit 16: Vital signs; pump and CGM downloads; assessment of infusion site reactions and  
691 occlusions; dispense trial product; dispensing of hypoglycemia/basal dose diary; drug  
692 accountability  
693  
694 Phone Visit 17: Ensure subject is changing insulin pump sites and CGM per protocol, assessment  
695 of infusion site reactions and occlusions; review of hypoglycemia (insulin titration if required)  
696  
697 Visit 18: Vital signs; pump and CGM downloads; assessment of infusion site reactions and  
698 occlusions; dispense trial product; dispensing of hypoglycemia/basal dose diary; drug  
699 accountability  
700  
701 Visit 19: Vital signs; pump and CGM downloads; assessment of infusion site reactions and  
702 occlusions; dispense trial product; dispensing of hypoglycemia/basal dose diary; drug  
703 accountability  
704  
705 Visit 20: Dexcom sensor insertion; assessment of infusion site reactions and occlusions, review  
706 of hypoglycemia/basal dose diary  
707  
708 Visit 21 (End of study visit): Vital signs; complete physical examination; review download of  
709 Dexcom and pump; HbA1c, GlycoMark, CBC, comprehensive metabolic profile (CMP), lipid  
710 panel, urine microalbumin/creatinine ratio (LabCorp); pregnancy test (urine); review treatment  
711 of hypoglycemia; insulin optimization for post-trial treatment; assessment of infusion site  
712 reactions and occlusions; drug accountability; treatment questionnaires  
713  
714 Phone Visit 22 (Follow-up phone visit): Capture AE's; review of hypoglycemia  
715

Trial Procedures	Screening	P2	Randomization	Treatment Period 1 (First treatment group)									Treatment Period 2 (Second treatment group)								EOT	F/U
				V4	V5	P6	V7	P8	V9	V10	V11	V12	V13	V14	P15	V16	P17	V18	V19	V20		
Visit (V), Phone (P)	V1	P2	V3	V4	V5	P6	V7	P8	V9	V10	V11	V12	V13	V14	P15	V16	P17	V18	V19	V20	V21	P22
Timing of Visit (Weeks)	-2	-1	0	2	4	6	8	10	12	16	18	20	22	24	26	28	30	32	36	38	40	44
Visit Window (Days)		+ 2	+ 1	+ 3	+ 3	+ 3	+ 3	+ 3	+ 3	+ 3	+ 2	+ 3	+ 3	+ 3	+ 3	+ 3	+ 3	+ 3	+ 3	+ 2	+ 3	+ 3
Informed Consent	X																					
In/Exclusion Criteria	X		X																			
Demography & Tobacco Use	X																					
Physical Examination	X											X									X	
Concomitant Illness /Medical History	X	X	X																			
Concomitant Medication	X	X	X	X	X	X	X	X	X	X	X	X	X	X	X	X	X	X	X	X	X	X
Child Bearing Potential	X																					
Pregnancy Test, Urine	X											X									X	
Height	X																					
Body Weight	X		X	X	X		X		X	X	X	X	X	X		X		X	X	X	X	X
Vital Signs	X		X	X	X		X		X	X	X	X	X	X		X		X	X	X	X	X
Dexcom Sensor Insertion	X	X									X										X	
CGM Download	X		X	X	X		X		X	X	X	X	X	X		X		X	X	X	X	X
Insulin Pump Download	X		X	X	X		X		X	X	X	X	X	X		X		X	X	X	X	X
Insulin Optimization			X	X	X							X	X	X								
Blood Sampling	X		X									X									X	
Point-of-Care HbA 1c			X																			
HbA 1c (central laboratory)	X											X									X	
GlycoMark	X											X									X	
CBC	X											X									X	
CMP	X											X									X	
Lipids	X																				X	
Urine MA	X											X									X	
Adverse Events				X	X	X	X	X	X	X	X	X	X	X	X	X	X	X	X	X	X	X
Hypoglycemia Assessment	X	X	X	X	X	X	X	X	X	X	X	X	X	X	X	X	X	X	X	X	X	X
Technical Complaints				X	X	X	X	X	X	X	X	X	X	X	X	X	X	X	X	X	X	X
Infusion Site Reactions				X	X	X	X	X	X	X	X	X	X	X	X	X	X	X	X	X	X	X
Infusion Site Occlusions				X	X	X	X	X	X	X	X	X	X	X	X	X	X	X	X	X	X	X
Randomization			X																			
Dispensing of Trial Product			X		X		X		X	X		X		X		X		X	X			
Drug Accountability					X		X		X	X		X		X		X		X	X		X	
Treatment Crossover												X										
Questionnaires/Surveys			X									X									X	
Diabetes Education	X	X	X	X	X	X	X	X	X	X	X	X	X	X	X	X	X	X	X	X	X	X
REMINDEES																						
Attend Visit Fasting	X											X										X

Degludec Pen Instruction			X*								X*											
Hand out Hypo/Basal Dose Diary	X		X	X	X		X		X	X	X	X	X	X		X		X	X	X		

\* Dependent upon to which treatment group the subject is assigned.

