## 185 **RATIONALE FOR THE STUDY POPULATION**

186

187 A population of well controlled patients with type 1 diabetes who are experienced in the use of

188 both CSII and CGM was chosen in order to assess the effect of the change in glycemic profile

189 using two different methods of basal insulin delivery. Studying a population with expertise in

190 diabetes self-management with these devices will minimize the effect of incorrect device use

191 and allow assessment of the effect of the change of insulin regimen itself. Allowing the subjects

192 to use their insulin pumps for bolus insulin delivery, as they are accustomed, will minimize the

193 chances of skipping meal boluses and correction doses.

194

195 Replacing basal insulin delivery by CSII with a single daily injection of degludec will add minimal,

196 if any, treatment burden which will be offset by potential therapeutic benefits. These benefits

197 include the potential for reduced glycemic variability and the elimination of the risk of

198 hyperglycemia and DKA with basal insulin interruption which can occur with infusion set  
199 occlusion or dislodgement inherent to CSII. Subjects may also enjoy the freedom afforded by a  
200 basal insulin injection which will allow them to disconnect from their pumps safely without  
201 sacrificing glycemic control for prolonged periods of time (which is not an option using CSII for  
202 basal insulin delivery).

203

204

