## 432 **DEFINITIONS**

### 433 **Adverse Event (AE):**

434 An AE is any undesirable medical event occurring to a subject in a clinical trial, whether or not  
435 related to the trial product(s). This includes events reported from the first trial related activity  
436 after the subject has signed the informed consent and until post treatment follow-up period as  
437 defined in the protocol. This will also include any events related to the malfunction of a  
438 medical device (i.e. an insulin pump or Dexcom CGM). The following will not be recorded as  
439 AEs, if recorded as medical history/concomitant illness on the CRF at screening:

- 440 • Pre-planned procedure, unless the condition for which the procedure was planned has
- 441 worsened from the first trial related activity after the subject has signed the informed consent
- 442 • Pre-existing conditions found as a result of screening procedures

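### The visit schedule asks by name about infusion-site harms only; degludec injection-site reactions and pen failures are left to general questioning, and any under-recording would favour degludec

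*Protocol*

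**What the plan says.** **Visit Procedures (visit list).** From Visit 4 to Visit 21, and also at Phone Visit 2, each entry includes an assessment of infusion-site reactions and occlusions; the Visit 4 entry reads in part "infusion site reactions and occlusions; dispensing of hypoglycemia/basal dose diary". No entry names an injection site or a pen problem.

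**Visit Procedures (opening note).** The note requires "capturing of AE's (including technical complaints and" (continuing on the next line) "device site reactions) will be performed at each study visit, as well as diabetes education". No device is named here.

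**Study flow sheet.** There are rows for "Infusion Site Reactions" and for infusion-site occlusions, and a separate row for "Technical Complaints". All three are marked from V4 to P22. There is no injection-site row and no general delivery-site row.

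**Definitions, Adverse Event.** The definition is broad: "An AE is any undesirable medical event occurring to a subject in a clinical trial, whether or not" related to trial product. It then adds malfunction of a "medical device (i.e. an insulin pump or Dexcom CGM". The pen is not mentioned.

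**Assessment of Subject Compliance.** Set occlusions are counted in both arms. The items recorded only for degludec are doses, times and missed injections, which describe adherence and not harm.

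**Rationale for the Study Population.** The protocol expects little extra burden from the injection: "Replacing basal insulin delivery by CSII with a single daily injection of degludec will add minimal", if any, treatment burden.

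**The concern.** The randomised contrast is the route of basal insulin, so local reactions and delivery failures are the harms most directly tied to it. The infusion set stays in place for boluses during the degludec period, so set problems are asked about by name under both treatments. What degludec adds is a daily injection and a pen, and the harms peculiar to those have no named question.

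General questions tend to elicit fewer events than specific ones. If that happens here, the shortfall falls on events that can arise only under degludec. The trial is open label, the hypothesis favours degludec, and the rationale already expects minimal added burden. The data handling section foresees safety analyses. An event that is never recorded cannot be restored by any later analysis, so this has to be settled when the data are collected.

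**Working it through.** The protocol gives no figure on this point to reproduce. The check is a count of prompts and a comparison of the wording in three places.

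**1. Count of named prompts**

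| Source | Infusion-site reactions and occlusions | Injection-site reactions or pen failure |
|---|---|---|
| Visit list | P2 and V4 to V21: 1 + 18 = 19 contacts | 0 |
| Flow sheet | V4 to P22: 19 contacts | 0 |
| In both | V4 to V21: 18 contacts | 0 |

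By treatment period, V4 to V12 (weeks 2, 4, 6, 8, 10, 12, 16, 18, 20) gives 9 contacts, and V13 to V21 gives another 9; 9 + 9 = 18. The two sources differ only at P2, before randomisation, and at P22, after treatment. The within-period count is the same in both.

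**2. Exposure that has no named prompt**

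One injection a day for 20 weeks is 20 × 7 = 140 injections per subject. For the planned 47 completers this is 140 × 47 = 6,580. These figures measure exposure, not harm.

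**3. Scope of the general prompts**

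- The opening note covers technical complaints and device site reactions with no device named. A pen failure fits the first term well. An injection site fits the second less readily, because the study devices listed under Study Drugs and Materials are pumps, with the Dexcom named next as the study CGM. The pen appears under packaging, as the form in which degludec is supplied.
- The flow sheet carries the technical complaints part over as its own row. The site part appears only as the two infusion-site rows, so the schedule is narrower than the note.
- The device clause in the adverse event definition mentions pump and CGM only.

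The three places therefore give three scopes: unnamed device, infusion site, and pump or CGM.

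**4. Direction and size**

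Infusion-site events are prompted identically in both periods, so that part of the record is balanced. The imbalance is confined to injection-specific events, which occur only on degludec; missing some of them can only lower the degludec count. The size would need the incidence of such events and the share that general questioning detects. The documents give neither.

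**The case against.** The case on the other side is substantial, and much of it stands.

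- A reader might infer that every site or device prompt is specific to the pump or CGM. The documents do not support that: the opening note and the technical complaints row name no device.
- A reader might infer that injection-site events are recorded only if the subject volunteers them. That also goes too far. Adverse events are captured at each visit, the definition covers any undesirable medical event, and complete physical examinations at V12 and V21 close each period and may show visible injection-site problems. Medication errors are events of special interest.
- A reader might infer that the record could never show degludec worse. It could: set problems, technical complaints and general adverse events are collected during degludec treatment too.
- The device clause extends the adverse event definition and does not restrict it. Elsewhere, in the exclusion criterion on rescreening, the protocol uses the same abbreviation loosely to introduce examples, so the omission of the pen may be drafting and not intent.
- The case report forms are not shown and may contain an injection-site item.
- No site-reaction or tolerability endpoint is listed, so no primary or secondary result is affected.

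What survives is narrower. Nothing in the protocol names the injection site or pen as something to ask about, while the corresponding infusion-set items are named at every contact in both periods. The general wording may catch some of these events, but it does not make the questioning equal, and the schedule that staff follow is less inclusive than the note above it.

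**Conclusion.** The point holds as an ascertainment gap with a known direction and an unknown size. Infusion-site harms are solicited by name at 9 contacts per period; injection-site reactions and pen failures are solicited by name at 0 and rely on general prompts and routine adverse event capture. Any under-recording would favour degludec.

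The documents do not show that events will in fact be lost, and they define no tolerability comparison that would be distorted, so it would be wrong to call a result biased. The conclusion rests on two assumptions: that the case report forms follow the protocol wording, and that a named question finds at least as many events as a general one. This is a worthwhile, inexpensive improvement, not a threat to the primary analysis.

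**What to change.** 1. In the visit list and flow sheet, replace the infusion-site reactions item with *insulin delivery site reactions (infusion set and injection site)*, asked in the same words at the same contacts in both periods. Keep set occlusions as they are.
2. In the adverse event definition, add the insulin pen and infusion set to the device clause, so that it agrees with the opening note of Visit Procedures.
3. Report delivery-site reactions and device failures by treatment, with infusion-set and injection or pen components shown separately. The separate display matters because the set is worn in both periods and the injection is given in only one.

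The cost is a wording change in three places and one extra checklist item on the paper form. No visit, procedure or staff is added. The likely downside is that recorded local reactions on degludec will rise, which should be read as fuller recording and not as a new safety signal.
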